3.3 Schedule of activities

See Section 13.6 for the SoA.

4 STATISTICAL HYPOTHESES

For each arms of Part 2, Arm 1A and 1B, the null hypothesis that the true response rate is 5% will be tested against a one-sided alternative (i.e. H_0 : ORR = 5% vs H_1 : ORR>5%). There will be no formal comparison between treatment groups. No further statistical hypothesis is under test.

Apart from this hypothesis, no formal statistical comparison between treatment groups will be performed for any of the other endpoints. All other p-values will be considered as supportive or explorative. The results of all other endpoints will be described with nominal p-values without any statement on statistical significance.

5 INTERIM ANALYSES AND ANALYSIS SEQUENCE

The interim analysis was performed based on all available data from the clinical data cut-off that will occur when the required number of patients in the respective arm had performed the first post-baseline tumor assessment or had been diagnosed with unequivocal clinical progression.

The final analysis of the trial will be performed based on all available data from a clinical data cut-off that will occur after patients in the respective setting of Part 2 (Arms 1A, 1B, and 2, 3) have completed 8 cycles of treatment or discontinued.

However, after the interim analysis, the enrollment of Part 2 Arms 1A and 1B (mCRPC) was stopped prior to the complete enrollment of the planned LPC patients. Therefore, the final analysis for mCRPC and the final analysis for LPC are planned to be performed separately.

The final analysis for mCRPC will be performed based on all available data from a clinical data cut-off that will occur after all the enrolled patients in Part 2 Arms 1A and 1B (mCRPC) have completed 8 cycles of treatment or discontinued.

The final analysis for patients with LPC will be performed based on all available data from a clinical data cut-off that will occur after all the planned patients in the Part 2 Arms 2 and 3 (LPC) have completed 8 cycles of treatment or discontinued.

Note: for both final analyses, the data from both LPC and mCRPC will be analyzed.

- At the final analysis for mCRPC, all the data for LPC up to the data cutoff for this analysis will also be analyzed.
- At the final analysis for LPC, all the data for mCRPC up to the data cutoff for this analysis will also be analyzed.

A further analysis, termed Follow-up analysis, will be performed when the last patient discontinues from the trial. For the Follow-up analysis only a subset of TFLs generated for the main analysis may be produced again, this analysis will include all new data collected in the database. All TFLs to be generated for the Follow-up analysis will be defined after the final analysis has been performed.

An Independent Data Monitoring Committee is not planned for this trial.

The patient's safety will be monitored throughout the trial by the SRC. The SRC will be chaired by the sponsor's Medical Monitor and membership will include at a minimum the trial principal investigators, members of the sponsor medical and safety departments, as well as additional staff as appropriate.

The SRC will review all DLTs and suspected unexpected serious adverse reactions, make the REDR recommendation at the end of the Dose Titration Part (Part 1) and periodically review safety and efficacy in Part 2. The SRC will make a recommendation to the sponsor after each meeting and how to proceed with the trial and whether to activate the respective expansion arms of the trial. The SRC will meet at least every 3 months throughout the trial.

The materials provided for review to the SRC, the SRC role and responsibilities and the general procedures (including communications) are defined and documented in the SRC charter (v4.0, dated 02 NOV 2020). The preparation of the review material for the SRC is not part of the SAP for this trial.

6 SAMPLE SIZE DETERMINATION

The sample size for Part 1 is driven by the 3+3+3 trial design and will range from 3 to 9 DLT evaluable patients depending on the number of DLTs which may occur. The main objective for the Part 2 is to perform exploratory biomarker analyses in the LPC setting and to preliminarily assess the efficacy in terms of response in the mCRPC setting.

Simon's two-stage design [5] based on the Minimax approach will be used for Part 2 Arm 1A and 1B separately. The null hypothesis that the true response rate is 5% will be tested against a one-sided alternative. In the first stage, 20 evaluable patients will be treated. Enrollment will continue following the sponsor's decision (upon recommendation from the SRC's review) and 13 evaluable patients may be treated for a total of 33 evaluable patients. If there are 1 or fewer responses in the first 20 evaluable patients, the enrollment for that arm may be stopped. The null hypothesis will be rejected if 5 or more responses are observed in 33 evaluable patients. This design yields a type I error rate of 2.5% and power of 80% when the true response rate is 20%.

A patient will be considered as evaluable if included in the primary analysis set (mITT set, see Section 7.1) which is defined as all patients who are randomized to the IMP and have a baseline and at least one post-baseline (i.e., one on-treatment or post-treatment) tumor assessment (clinical or imaging assessment).

No formal sample size calculation is performed for the LPC setting in Part 2 (Arms 2 and 3) due to its exploratory nature. However, 20 patients are planned to be enrolled into Arm 2 and Arm 3. Based on this sample size (N=20) the one-sided 95% CI of binary

endpoints will have a width of up to +/-0.19 in each group depending on the observed effect size.

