#### Sample Size Determination

The sample size for Part 1 is driven by the 3+3+3 trial design and will range from 3 to 9 DLT evaluable patients depending on the number of DLTs which may occur. The main objective for the Part 2 is to perform exploratory biomarker analyses in the LPC setting and to preliminary assess the efficacy in terms of response in the mCRPC setting.

Simon's two-stage design (Simon, 1989) based on the Minimax approach will be used for Part 2 Arm 1A and 1B separately. The null hypothesis that the true response rate is 5% will be tested against a one-sided alternative. In the first stage, 20 evaluable patients will be treated. Enrollment will continue following sponsor decision (upon recommendation from the SRC following review) and 13 additional evaluable patients may be treated for a total of 33 evaluable patients. If there is one or fewer responses in the first 20 evaluable patients, the enrollment for that arm may be stopped. The null hypothesis will be rejected if five or more responses are observed in 33 evaluable patients. This design yields a type I error rate of 2.5% and power of 80% when the true response rate is 20%.

A patient will be considered as evaluable if included in the primary analysis set (mITT set) which is defined as all patients who are randomized to the IMP and

CONFIDENTIAL Page 23 of 122

have a baseline and at least one post-baseline (i.e., one on-treatment or post-treatment) tumor assessment (clinical or imaging assessment).

No formal sample size calculation is performed for the LPC setting in Part 2 (Arms 2 and 3) due to its exploratory nature. However, 20 patients are planned to be enrolled into Arm 2 and Arm 3. Based on this sample size (N=20) the one-sided 95% CI of binary endpoints will have a width of up to +/-0.19 in each group depending on the observed effect size.

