# **9.2.** Sample Size Determination

The sample size for Part 1 is driven by the 3+3+3 trial design and will range from 3 to 9 DLT evaluable patients depending on the number of DLTs which may occur. The main objective for the Part 2 is to perform exploratory biomarker analyses in the LPC setting and to preliminary assess the efficacy in terms of response in the mCRPC setting.

Simon's two-stage design (Simon, 1989) based on the Minimax approach will be used for Part 2 Arm 1A and 1B separately. The null hypothesis that the true response rate is 5% will be tested against a one-sided alternative. In the first stage, 20 evaluable patients will be treated. Enrollment will continue following sponsor decision (upon recommendation from the SRC following review) and 13 evaluable patients may be treated for a total of 33 evaluable patients. If there is one or fewer responses in the first 20 evaluable patients, the enrollment for that arm may be stopped. The null hypothesis will be rejected if five or more responses are observed in 33 evaluable patients. This design yields a type I error rate of 2.5% and power of 80% when the true response rate is 20%.

A patient will be considered as evaluable if included in the primary analysis set (mITT set, see Section 9.3) which is defined as all patients who are randomized to the IMP and have a baseline

CONFIDENTIAL Page 82 of 122

and at least one post-baseline (i.e., one on-treatment or post-treatment) tumor assessment (clinical or imaging assessment).

No formal sample size calculation is performed for the LPC setting in Part 2 (Arms 2 and 3) due to its exploratory nature. However, 20 patients are planned to be enrolled into Arm 2 and Arm 3. Based on this sample size (N=20) the one-sided 95% CI of binary endpoints will have a width of up to  $\pm$ 0.19 in each group depending on the observed effect size.

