7 ANALYSIS SETS AND SUBGROUPS

7.1 Analysis sets

The following analysis sets are defined:

Population	Description
Screened	The screened analysis set is defined as all patients who sign the informed consent form (ICF).
Intent-to-Treat (ITT)	Part 1: The ITT set is defined as all patients to whom IMP is assigned. Part 2: The ITT set is defined as all patients who are randomized to the IMP.
Modified Intent-to-Treat (mITT)	Part 1: The mITT set is defined as all patients to whom IMP is assigned and have a baseline and at least one post-baseline (i.e., one on-treatment or post-treatment) tumor assessment (clinical or imaging assessment). Part 2: The mITT set is defined as all patients who are randomized to the IMP and have a baseline and at least one post-baseline (i.e., one on-treatment or post-treatment) tumor assessment (clinical or imaging assessment).
Safety (SAF)	The safety set is defined as all patients who have received IMP (i.e., at least 1 dose of W_pro1 and/or cemiplimab).
DLT Evaluation	Only applicable for Part 1: The DLT evaluation set includes all patients from the safety set who either have completed the DLT evaluation period and meet the minimum exposure criterion or have experienced a DLT during C1. Patients who do not experience any DLTs during C1 are considered to be evaluable if they have been observed for a minimum of 21 days following the first dose and are considered to have sufficient safety data to conclude that a DLT did not occur. A patient is considered to have met the minimum exposure criterion if the relative dose intensity of W_pro1 in C1 is at least 90%.
Per Protocol (PP)	The per protocol (PP) set is defined as all patients who have received IMP and fulfil the following criteria: 
 • The absence of any important protocol deviations that could affect the primary efficacy analysis • The completion of a minimal exposure to the treatment of 1 cycle • Availability of baseline and at least one on-treatment / post-treatment tumor assessment Important deviations will lead to an exclusion of patients from the PP set and will be agreed at the data review meeting (DRM) prior to database snapshot for the final analysis. Protocol deviations that may be considered important will be specified in the SAP (see Section 7.2)

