The number and percentage of patients per PSADT under-treatment on C4D1 and D1 of every fourth subsequent cycle (e.g., C8D1, C12D1, etc.) in Part 1 and Part 2 Arm 1A and 1B, or on C4D1, C8D1, and EoT in Part 2 Arms 2 and 3 compared with baseline. For more details for the calculation of PSADT, see Section 8.2.

The following categorization of PSADT should be reported: 0 - 3 months, >3 – 6 months, >6 – 9 months, >9 – 12 months, >12 – 18 months, >18 – 24 months, >24 months.

Sensitivity analyses will be performed using the ITT set and the PP set depending on the number of patients excluded.

Objective Response Rate for Part 1

For Part 1, ORR is defined as secondary efficacy endpoint as best objective response per PCWG3 and will be analyzed descriptively for the mITT set. For more details, see Section 8.7.1.1.

Tumor assessment post-treatment compared to baseline for Part 2, Arm 2 and Arm 3

Tumor measurements using mpMRI or, if tumor measurement is not feasible with a mpMRI, imaging according to local practice (e.g. CT or MRI), should be performed at the following time points:

- During the screening period (within 28 days before C1D1 (baseline))
- Prior to surgery (i.e. at the end of C8/EoT Visit)

Tumor response will be assessed based on Radiological Soft Tissue Evaluation at both time points. Number of patients in each category and ORR will be summarized with absolute and relative frequencies along with two-sided 95% Clopper-Person CIs by treatment group for the mITT set.

Tumor response assessment including overall response, best overall response and clinical progression as documented in the eCRF will be listed. In addition, listings including all tumor assessments per PCWG3 (target lesion, non-target lesion, new lesion) will be generated.

Sensitivity analyses will be performed using the ITT set and the PP set depending on the number of patients excluded.

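### The LPC precision statement (one-sided 95%, up to ±0.19 at N=20) does not describe the two-sided exact interval the SAP plans, whose half-width reaches 0.228

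*SAP*

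**What the plan says.** SAP section 6 makes no formal sample size calculation for the LPC setting. It states that "20 patients are planned to be enrolled into Arm 2 and Arm 3" and then describes what that number achieves: for a one-sided 95% interval, binary "endpoints will have a width of up to +/-0.19 in each group depending on the observed effect size". The protocol carries the same statement in the synopsis and in section 9.2 ("Based on this sample size (N=20) the one-sided 95% CI of binary endpoints will have a width of" up to ±0.19).

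The LPC analysis itself is set out in SAP section 8.7.3.1, under tumor assessment for Arms 2 and 3. The response categories and ORR are to be reported with "absolute and relative frequencies along with two-sided 95% Clopper-Person CIs by treatment group for the mITT set".

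SAP section 7.1 defines the denominator for Part 2: "The mITT set is defined as all patients who are randomized to the IMP and have a baseline and at least one post-baseline" tumor assessment, which may be clinical or by imaging. Section 8.7.3.1 schedules LPC tumor measurement at screening and once afterwards, before surgery.

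**The concern.** Section 6 and section 8.7.3.1 describe different intervals. One is one-sided with 5% in the tail; the other is two-sided and exact, with 2.5% in each tail. The SAP text plans no one-sided interval for any LPC endpoint. The PSA categories in section 8.7.3.1 are counts and percentages only, and the Greenwood intervals in section 8.1 are for time-to-event rates. The notation adds to the confusion, because ± does not describe a one-sided interval and invites the reader to take 0.19 as the half-width of an ordinary 95% interval.

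The denominators differ as well: section 6 counts patients enrolled, and section 8.7.3.1 counts patients in the mITT set.

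With no formal LPC sample size, this sentence is the only quantitative statement of what 20 patients per arm can show. A reader who sets it against the reported LPC intervals will find them wider than the plan said.

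**Working it through.** **Inputs**

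- n = 20 per LPC arm, as enrolled (SAP section 6).
- Stated interval: one-sided 95%, so 5% in the tail, z = 1.645 (SAP section 6).
- Planned interval: two-sided 95% Clopper-Pearson, 2.5% per tail, mITT set (SAP section 8.7.3.1).
- Observed proportion 0.5 for the stated figure. This is an assumption: it is the worst case for an upper bound, and the documents give no LPC response rate.

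**Step 1. Reproduce the stated 0.19**

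The documents give no formula. Three common approximations at p = 0.5:

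- z × √(0.25/20) = 1.645 × 0.1118 = 0.184
- z × √(0.25/19) = 0.189
- t (19 df) × √(0.25/20) = 0.193

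The second and third round to 0.19 and the plain Wald value rounds to 0.18. The stated figure is therefore reachable as a one-sided approximate bound.

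**Step 2. Compute the planned interval at n = 20**

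For x responders, lower = Beta quantile(0.025; x, n−x+1), upper = Beta quantile(0.975; x+1, n−x), and half-width = (upper − lower)/2.

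| Responders | 95% limits | Half-width | Longer side |
|---|---|---|---|
| 4/20 | 0.0573 to 0.4366 | 0.1896 | 0.2366 |
| 5/20 | 0.0866 to 0.4910 | 0.2022 | 0.2410 |
| 6/20 | 0.1189 to 0.5428 | 0.2119 | 0.2428 |
| 8/20 | 0.1912 to 0.6395 | 0.2241 | 0.2395 |
| 10/20 | 0.2720 to 0.7280 | 0.2280 | 0.2280 |

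The results are symmetric about 10/20. The maximum half-width is 0.228, at 10/20. The half-width exceeds 0.19 from 5 to 15 responders and stays within it for 0 to 4 and 16 to 20. The longest single side is 0.243, at 6/20 (upper) or 14/20 (lower).

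**Step 3. Size of the gap and where it comes from**

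- Total: 0.228 − 0.190 = 0.038, and 0.038/0.19 = 20%.
- The exact method with 5% per tail gives 0.302 to 0.698 at 10/20, a distance of 0.198. Approximate versus exact therefore accounts for 0.198 − 0.190 = 0.008.
- Moving from 5% to 2.5% per tail accounts for 0.228 − 0.198 = 0.030.

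This split starts from the rounded 0.19. With the exact method kept at one-sided 95%, the largest distance is 0.208 (7/20 upper, 13/20 lower), also above 0.19.

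**Step 4. Effect of a smaller mITT set**

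The documents give no LPC mITT count, so these counts are assumed.

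| mITT patients | Maximum two-sided half-width |
|---|---|
| 19 | 0.233 |
| 18 | 0.240 |
| 17 | 0.246 |
| 16 | 0.253 |

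**The case against.** The strongest reply is that nothing is false on its own terms. Section 6 labels its interval one-sided, its figure can be reproduced, and a planning statement at one level can coexist with a reporting interval at another. Within the protocol there is no visible conflict, because section 9.4.3 names LPC tumor response as an endpoint without giving an interval. It remains the case that the planning sentence describes an interval the SAP text never produces, for the endpoint where it would be used.

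The denominator argument has limits. A clinical assessment also qualifies a patient for the mITT set, so a missed scan does not by itself exclude him. Drop-outs may be replaced (protocol section 4.2). The LPC schedule of activities also allows tumor assessment at unscheduled visits and, optionally, at end of treatment and surgery. A count below 20 is therefore possible, but its size is unknown.

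Table shells are in a separate document, and the immunogenicity and most biomarker analyses lie outside this SAP. The claim that this is the only LPC binary interval therefore covers the SAP text alone. The 20% is also the worst case, at 10/20. Finally, the arms are exploratory and nothing is decided on this figure. That is a reason to rate the point minor, but it does not remove the mismatch.

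**Conclusion.** The concern holds as an inconsistency of minor weight. The stated ±0.19 belongs to a one-sided approximate bound, while the planned LPC interval is two-sided and exact. Its half-width is up to 0.228 at n=20, and one limit can lie up to 0.243 from the estimate. These figures assume that all 20 patients per arm are in the mITT set; any exclusions make the interval wider. ITT and PP sensitivity analyses may also be run, but the SAP specifies no other interval type for them. N=20 was not derived from the 0.19, and the formal hypotheses concern Arms 1A and 1B only, so no conclusion of the trial depends on it.

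**What to change.** Replace the LPC precision sentence in SAP section 6 with:

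> With 20 evaluable patients per arm, the two-sided 95% Clopper-Pearson interval for a binary endpoint has a half-width of up to 0.23 (0.27 to 0.73 at 10/20), and is wider if fewer than 20 patients are in the mITT set (for example, up to 0.24 with 18).

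Align the matching sentences in the protocol synopsis and section 9.2 when the protocol is next amended. SAP version 2.0 still has the LPC final analysis ahead of it (section 5), so the correction can precede the results. It changes no analysis, table, sample size or decision; the only cost is a slightly less favourable statement of LPC precision.

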7 ANALYSIS SETS AND SUBGROUPS

7.1 Analysis sets

The following analysis sets are defined:

Population	Description
Screened	The screened analysis set is defined as all patients who sign the informed consent form (ICF).
Intent-to-Treat (ITT)	Part 1: The ITT set is defined as all patients to whom IMP is assigned. Part 2: The ITT set is defined as all patients who are randomized to the IMP.
Modified Intent-to-Treat (mITT)	Part 1: The mITT set is defined as all patients to whom IMP is assigned and have a baseline and at least one post-baseline (i.e., one on-treatment or post-treatment) tumor assessment (clinical or imaging assessment). Part 2: The mITT set is defined as all patients who are randomized to the IMP and have a baseline and at least one post-baseline (i.e., one on-treatment or post-treatment) tumor assessment (clinical or imaging assessment).
Safety (SAF)	The safety set is defined as all patients who have received IMP (i.e., at least 1 dose of W_pro1 and/or cemiplimab).
DLT Evaluation	Only applicable for Part 1: The DLT evaluation set includes all patients from the safety set who either have completed the DLT evaluation period and meet the minimum exposure criterion or have experienced a DLT during C1. Patients who do not experience any DLTs during C1 are considered to be evaluable if they have been observed for a minimum of 21 days following the first dose and are considered to have sufficient safety data to conclude that a DLT did not occur. A patient is considered to have met the minimum exposure criterion if the relative dose intensity of W_pro1 in C1 is at least 90%.
Per Protocol (PP)	The per protocol (PP) set is defined as all patients who have received IMP and fulfil the following criteria: 
 • The absence of any important protocol deviations that could affect the primary efficacy analysis • The completion of a minimal exposure to the treatment of 1 cycle • Availability of baseline and at least one on-treatment / post-treatment tumor assessment Important deviations will lead to an exclusion of patients from the PP set and will be agreed at the data review meeting (DRM) prior to database snapshot for the final analysis. Protocol deviations that may be considered important will be specified in the SAP (see Section 7.2)
Pharmacodynamic	The pharmacodynamic set is defined as all patients who have received IMP (i.e., at least 1 dose of W_pro1 and/or cemiplimab) and with a baseline and at least 1 on-treatment/post-treatment follow-up

Population	Description
	pharmacodynamic assessment as specified in Section 8.8.1 (i.e. Hormones (Testosterone), Cytokines).
Subsequent Cemiplimab Monotherapy on Progression (Cemi Mono on PD)	Only applicable for Part 2 Arm 1B: The subsequent cemiplimab monotherapy on progression set (Cemi Mono on PD) is defined as all mCRPC patients in Arm 1B (W_pro1 monotherapy) who switch to cemiplimab monotherapy after disease progression and who received at least one dose of cemiplimab.

The DLT evaluation set will be used for the evaluation of DLTs in order to assess the REDR in Part 1 of the trial.

The safety set will be used for all other safety analyses, while the mITT set will be used as primary analysis set for efficacy analyses.

The subsequent cemiplimab monotherapy on progression set will be used for all exploratory safety and efficacy analyses for the Arm 1B patients who received cemiplimab (i.e., at least 1 dose of cemiplimab) after progression to W_pro1 monotherapy.

The ITT analysis set will be used for disposition analyses.

Further, the ITT and PP sets will be used for sensitivity analyses of some predefined efficacy endpoints depending on the number of patients excluded. If none of the patients are excluded from the mITT set, compared to the ITT set, or if the number of patients excluded from the PP set is small (exclusion rate $\leq 10\%$), no additional sensitivity analyses for the ITT or the PP set will be generated. The final decision to perform sensitivity analyses for the ITT set or for the PP set will be made during the DRM meeting for the final analysis.

All safety analyses and analyses based on the Pharmacodynamic set will be based on the treatment actually taken by the patient (“as treated”).

All other analyses will be based on the treatment the patient was assigned/randomized to (“as randomized”), unless stated otherwise.

